7. STUDY DESIGN

7.1. Study Overview

This is a prospective, noninterventional, multicenter, observational study in patients who are beginning Fampyra treatment in the postmarketing setting. The decision to enroll a patient into this study will not be made until after the neurologist and patient have decided to begin Fampyra treatment and Fampyra has been prescribed.

The study will be conducted in postmarketing routine practice setting. The study will expand the number and spectrum of patients treated with Fampyra to be observed to help further understand the safety profiles of Fampyra in subpopulations not fully studied during the development phase, and to increase understanding of the specific safety issues described above. As such, this observational study will assess the effectiveness of risk minimization measures, as specified in the risk management plan for Fampyra.

Prescribing neurologists will be invited to participate in the study as Investigators. During the study, the Investigators should treat patients according to local clinical practice in line with the SmPC. Under the protocol, the Investigators are not required to perform any medical procedures that are outside of their normal clinical practice. Any cases of lack of efficacy or deterioration of a patient's health should be diagnosed and managed as per local guidelines.

Data will be collected at the Enrollment Visit (Baseline) and during the Follow-Up period (i.e., Baseline until approximately 1 year after Enrollment). Follow-Up visits should occur according to routine local clinical practice, with data collection possible at any timepoint during this period. A study site may consider a patient lost to follow-up after 3 failed documented contact attempts by the site staff (one of which must be a certified letter). Data to be collected for this noninterventional study are shown in Section 4.1 and Section 4.2. The study procedures are described in Section 10. All patient visits will be documented in the case report form (CRF).

7.2. Overall Study Duration and Follow-Up

The planned duration of observation for each patient is approximately 1 year. Patients who discontinue Fampyra, regardless of the reasons and time of discontinuation, will be encouraged to remain in the study for the full 1-year observation period, unless the patients withdraw consent to participate in the study.

7.3. Study Centers

Approximately 300 study centers will be initiated in multiple countries outside the US. Countries will be included based on the status of the marketing authorization and commercial availability of Fampyra.

The study will be proposed to neurologists based in secondary care settings or in private practice in the community as appropriate for individual countries.

CONFIDENTIAL

The information contained herein may not be used, disclosed, or published without the written consent of Biogen Idec MA Inc.

7.4. End of Study

The end of study will be the last patient's last visit or telephone contact. Final statistical analysis will be performed once the database is locked.

CONFIDENTIAL

The information contained herein may not be used, disclosed, or published without the written consent of Biogen Idec MA Inc.

8. PATIENT CHARACTERISTICS AND PRINCIPLES OF INCLUDING PATIENTS

8.1. Number and Characterization of Patients

Approximately 5000 MS patients who are prescribed Fampyra will be enrolled prior to initiation of their Fampyra treatment.

The decision to enroll a patient into the study will not be made until after the decision regarding therapy has been made and Fampyra has been prescribed.

8.2. Principles of Enrollment Into the Fampyra Observational Study

To be eligible to participate in this observational study, patients must fulfil the following eligibility criteria at the time of Enrollment:

1. Patients who have been newly prescribed Fampyra according to the terms of the marketing authorization, but who have not yet started treatment with Fampyra.
2. Patients who are willing and able to provide written informed consent.

8.3. Enrollment of Patients

The Investigators will be asked to invite eligible patients who are about to begin treatment with Fampyra to participate in the study.

Patients will be enrolled after the Investigator has verified that they are eligible per criteria in Section 8.2. At the Enrollment Visit, enrolled patients prescribed Fampyra will be assigned a unique patient identification number. This number will be used to track the patient throughout the study.

Any patient identification numbers that are assigned will not be reused even if the patient does not start Fampyra treatment.

An individual study patient may only be included once in the study. Patients who completed the study and patients who withdraw consent and/or complete the Early Treatment/Study Discontinuation Visit will not be eligible for re-enrollment.

CONFIDENTIAL

The information contained herein may not be used, disclosed, or published without the written consent of Biogen Idec MA Inc.

9. TREATMENT OF PATIENTS

9.1. Fampyra Treatment

Fampyra is commercially available and is a prolonged-release tablet containing 10 mg active substance 4-AP and excipients.

Fampyra will not be supplied for this study. The Investigators will follow standard local procedures for prescribing commercial Fampyra. No reference therapies will be included in the study.

9.2. Fampyra Administration

The decision to administer commercially available Fampyra is the responsibility of the treating neurologist according to his/her medical judgment. The decision to treat a patient with Fampyra must be made prior to considering enrolling the patient into the study. Study neurologists (Investigators) are not required to perform any medical procedures that are outside of the local clinical practice or the prescribing information. Any cases of lack of efficacy or deterioration of a patient's health should be diagnosed and managed as per local PI. If decline in walking ability is observed, physicians should consider an interruption to treatment in order to reassess the benefits of Fampyra. The re-evaluation should include withdrawal of Fampyra and performing the walking test. Fampyra should be discontinued if patients no longer receive walking benefit.

9.3. Concomitant Therapies and Procedures

In addition to Fampyra, any other treatments or procedures that are considered necessary for the patient's welfare may be given at the discretion of the Investigator. Administration of continuous concomitant procedures and medications (including herbals and nutraceuticals) must be reported in the appropriate section of the CRF along with reasons for use. Continuous concomitant procedures and medications are defined as a treatment administered regularly for 2 weeks or more. The generic names for concomitant medications should be recorded, if possible. The total daily dose should be recorded in the CRF whenever possible.

9.4. Continuation of Fampyra Treatment

Following completion of the study, patients can continue to be treated with Fampyra according to normal clinical practice.

CONFIDENTIAL

The information contained herein may not be used, disclosed, or published without the written consent of Biogen Idec MA Inc.

10. STUDY PROCEDURE

Following the decision to treat a patient with Fampyra, his/her suitability for enrollment into the study must be assessed according to the enrollment principles described in Section 8.2. Enrolled patients will undergo the assessments at Baseline and any timepoint during the Follow-Up period according to routine practice, as listed in Section 4.1 and Section 4.2 and defined below.

10.1. Enrollment (Baseline)

The Investigator will collect the following data at the Enrollment Visit (Baseline):

- assessment of eligibility for the Fampyra observational study
- informed consent for participating in the Fampyra observational study
- demographic data
- record creatinine clearance if serum creatinine is already available per normal practice (not specifically performed for the study)
- obtain urine culture (if available)
- medical history (in reference to the time prior to enrollment): assessment of clinically significant medical and surgical history and concomitant diseases (collected according to body system codes); known cardiovascular risk factors: the presence or absence of specific cardiovascular risk factors (e.g., conduction disorder, left-ventricular hypertrophy, coronary heart disease, hypertension, alcohol abuse, stress, smoking); MS disease classification
- assessment and recording of EDSS [Kurtzke 1983]
- previous (past 6 months) and current treatment (if any) for the underlying MS disease: use and duration including, but not limited to, disease-modifying, antineoplastic, or other immunosuppressive medications and systemic steroids
- continuous concomitant procedures and medications, including herbal preparations and nutraceuticals (defined as a treatment used regularly for ≥ 2 weeks)
- Fampyra treatment: dose, indication, reason for use, and start date (if started on the day of enrollment, otherwise record start date at the next visit). Information on previous exposure to any formulations of fampridine prior to Enrollment should be recorded.
- patient assessment of physical and psychological impact of MS using MSIS-29

10.2. Postenrollment Follow-Up

Data will be collected during the Follow-Up period: approximately 1 year after Enrollment. Follow-Up visits should occur according to clinical practice, with data collection possible at any timepoint during this period, either by telephone contact (except CGI-I) or during routine local clinical practice site visits. The following data will be collected during this period:

CONFIDENTIAL

The information contained herein may not be used, disclosed, or published without the written consent of Biogen Idec MA Inc.

- record creatinine clearance if serum creatinine is already available per normal practice (not specifically performed for the study)
- obtain urine culture (if available)
- status of treatment with Fampyra: dose, start and stop date (if applicable), and date of dosage change or interruption, or date of discontinuation
- changes in continuous concomitant therapies
- SAEs, AEs leading to Fampyra dosage change or discontinuation, AEs experienced by the patient at the time of Fampyra overdose, instances of overdose, and AEs of particular interest (see Section 11.2.2)
- Physician's CGI-I of walking ability (needs to be assessed during clinical visit, not by telephone)

A neurological assessment of walking may be conducted, in line with the SmPC or other local prescribing information.

Additionally, MS patients will be asked to complete assessments of physical and psychological impact of MS using MSIS-29.

Throughout the study, female patients of childbearing potential should be asked about their pregnancy status and possible pregnancies/spontaneous abortions since their last consultation with their neurologist. See Section 11.2.5 for reporting pregnancies/spontaneous abortions.

Data will be collected as above for all patients, including those who are followed up after early discontinuation of Fampyra treatment (see Section 7.2).

10.3. Treatment/Study Discontinuation Visit

If a patient's participation in the Fampyra observational study is discontinued early, the Investigator must make every attempt to contact the patient in order to collect information specified in Early Treatment/Study Discontinuation Visit in Section 4.1 and Section 4.2. Patients can continue on study even after terminating treatment. If a patient is discontinued from the study, then both the End of Treatment and End of Study CRFs should be completed. If the patient discontinued treatment early, but continued in the study, then the End of Treatment CRF should be completed as soon as possible after terminating treatment, and the End of Study CRF should be completed at the conclusion of the study.

10.4. Lost to Follow-Up

A site may consider a patient lost to follow-up after 3 failed documented contact attempts, one of which must be a certified letter.

10.5. Replacements

Study patients who prematurely discontinue participation will not be replaced.

CONFIDENTIAL

The information contained herein may not be used, disclosed, or published without the written consent of Biogen Idec MA Inc.

10.6. Patient Transfers

Study patients who change their place of residence may continue follow-up with a participating clinical site close to their new location, if one is available. This applies to both permanent moves and extended stays away from home such as college attendance or long-term job assignments that are expected to last for the remaining duration of follow-up.

10.7. Data Handling

Whenever possible, an electronic CRF will be used to store and transmit patient information. Access to electronic CRFs will be strictly password protected and limited to personnel directly participating in the study. The file structure and format for the CRF will be provided by Biogen Idec or their representative and should be handled in accordance with the instructions provided.

The CRF must be completed as soon as possible after any patient evaluation or communication. If data need to be changed due to erroneous input or for other reasons, an electronic audit will track these changes. The CRFs and computers that store them must be accessible to study monitors and other regulatory auditors.

The CRF must be reviewed, signed (electronically, if appropriate), and dated by the Investigator.

CONFIDENTIAL

The information contained herein may not be used, disclosed, or published without the written consent of Biogen Idec MA Inc.

11. SAFETY DEFINITIONS, MONITORING, AND REPORTING

Throughout the course of the study, every effort must be made to remain alert to possible SAEs, AEs leading to dosage change or discontinuation of Fampyra, AEs experienced by the patient at the time of Fampyra overdose, instances of overdose (even without an AE), and AEs of particular interest (see Section 11.2.2).

11.1. Definitions

11.1.1. Adverse Event

An AE is any untoward medical occurrence in a patient or clinical investigation patient administered a pharmaceutical product and that does not necessarily have a causal relationship with this treatment. An AE can therefore be any unfavorable and unintended sign (including an abnormal laboratory finding), symptom, or disease temporally associated with the use of a medicinal product, whether or not related to the medicinal product.

11.1.2. Serious Adverse Event

An SAE is any untoward medical occurrence that at any dose:

- results in death
- in the view of the Investigator, places the patient at immediate risk of death (a life-threatening event); however, this does not include an event that, had it occurred in a more severe form, might have caused death
- requires inpatient hospitalization or prolongation of existing hospitalization
- results in persistent or significant disability/incapacity, or
- results in a congenital anomaly/birth defect.

An SAE may also be any other medically important event that, in the opinion of the Investigator, may jeopardize the patient or may require intervention to prevent one of the other outcomes listed in the definition above. (Examples of such medical events include allergic bronchospasm requiring intensive treatment in an emergency room, or convulsions occurring at home that do not require an inpatient hospitalization.)

For the purpose of this study, all seizures and spontaneous abortions will be considered SAEs.

11.1.3. Overdose

An overdose is any dose of Fampyra given to a patient or taken by a patient that exceeds the dose described in the local Fampyra label, PI, or prescription information. All incidences of overdose, with or without any symptoms or signs, will be recorded. Symptoms or signs experienced by the patient at the time of overdose will be reported as AEs (see AE categories to be reported in Section 11.2.2).

CONFIDENTIAL

The information contained herein may not be used, disclosed, or published without the written consent of Biogen Idec MA Inc.

11.2. Monitoring and Recording Events

11.2.1. Serious Adverse Events

Regardless of whether the patient continues on Fampyra treatment or not, any SAE experienced by an enrolled patient between the time of the first dose of Fampyra and Study Completion (approximately 1 year after the first dose) or Early Study Discontinuation Visit is to be recorded on the SAE form, regardless of the severity of the event or its relationship to Fampyra treatment. For reporting timelines and procedures, see Section 11.2.4.

11.2.2. Adverse Events

The Investigators should review all AEs and record the following events in the CRF:

- SAEs (including all seizures and spontaneous abortions)
- AEs leading to Fampyra dosage change or discontinuation
- AEs experienced by the patient at the time of Fampyra overdose
- AEs of particular interest
 - symptoms of UTI, including results of urine culture where possible
 - depression and suicide attempt
 - cardiac disorders
 - severe infections other than UTI
 - anxiety
 - events suggestive of central nervous system stimulation (insomnia, dizziness, paresthesia, balance disorder, dyskinesia, falls, anxiety, sleep disorder, agitation, psychosis, hallucinations, tremor, trigeminal neuralgia, neuralgia, dysesthesia, sensory disturbance, muscle spasms, muscle twitching, and irritability)
 - clinically significant hematologic abnormalities

All other non-serious AEs will not be collected as part of this study and should follow spontaneous postmarketing reporting rules as per local regulations.

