5.2. Study Rationale

Due to the inherent constraints of clinical trials, the existing Fampyra safety database established during the development phase has its limitations, for example, the number of patients aged ≥ 65 years was limited and patients with pre-existing cardiovascular risk factors were excluded from the studies. Therefore, understanding of safety issues in these patient subpopulations is limited. It is expected that these patients will be represented in this observational study to be conducted in postmarketing routine practice setting and will help understand the safety profiles in these subpopulations not yet fully studied during the development phase.

Specifically, premarketing clinical trials were not powered to evaluate the incidence of rare AEs, including seizure. This observational study is powered to detect a doubling in the incidence of seizures in the MS patient population to further assess if Fampyra treatment is associated with an increased seizure rate.

Furthermore, a 3.6% higher incidence of urinary tract symptoms (8.4% in placebo-treated patients versus 12.0% in Fampyra-treated patients) was observed based on data from 3 pooled premarketing placebo-controlled clinical trials; however, it is not fully understood if the event was a result of infection or sensory overstimulation. This study is also aimed to improve quantification of urinary tract symptoms as either culture-confirmed infection or culture-negative symptomatology.

CONFIDENTIAL

The information contained herein may not be used, disclosed, or published without the written consent of Biogen Idec MA Inc.

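### The urinary event collected in Section 11.2.2 is narrower than, or at best ambiguous against, the Section 5.2 aim of classifying all urinary tract symptoms by culture result

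*Protocol*

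**What the plan says.** Section 5.2 of the protocol reports urinary tract symptoms in 12.0% of Fampyra-treated and 8.4% of placebo-treated patients in three pooled premarketing trials. It says that "it is not fully understood if the event was a result of infection or sensory overstimulation" and that the study is meant to "improve quantification of urinary tract symptoms as either culture-confirmed infection or culture-negative symptomatology". The synopsis raises the same open question.

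Section 11.2.2 lists what investigators record. The one urinary entry among the events of particular interest is "symptoms of UTI, including results of urine culture where possible". The section closes with: "All other non-serious AEs will not be collected as part of this study". A non-serious urinary symptom outside that entry can still come in under "AEs leading to Fampyra dosage change or discontinuation" or "AEs experienced by the patient at the time of Fampyra overdose".

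Section 11.2.3 requires recording whatever the severity or relationship to treatment, but only for events that Section 11.2.2 already defines. Urine culture is recorded if available (Sections 4.1, 10.1 and 10.2).

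**The concern.** The aim is stated for symptoms of either origin. The collection item is named after one of the two origins. A neurologist who sees new urgency or frequency and puts it down to MS or to the drug may reasonably decide that it is not a symptom of UTI and leave it out. Whether an event enters the data can then depend on the suspected cause, which is what the study is meant to clarify.

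Two results are at stake: the total incidence of urinary symptoms and the split between infective and non-infective cases. The study has no reference therapy (Section 9.1), and Section 12.4 compares incidence with published data and other sources. A count limited to suspected UTI would not be like for like with the premarketing figures for urinary tract symptoms. With about 300 centers in several countries, an undefined term may also be read differently from site to site. An event that was never entered cannot be added by any later analysis plan.

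**Working it through.** **The protocol's own figure.** 12.0% − 8.4% = 3.6 percentage points, as Section 5.2 states. This point disputes no sample size or power figure.

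**Does another part of the protocol widen the urinary item?**

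- *Section 11.2.3* refers back to the events defined in Section 11.2.2, so it carries the same term.
- *The central nervous system stimulation item in Section 11.2.2* names 19 events, none of them urinary. The nearest, sensory disturbance, is unspecific.
- *Serious events, dosage change or discontinuation, and overdose* capture a urinary symptom whatever its cause, but only where it has that consequence or arises in that circumstance.
- *MSIS-29 item 20 (Appendix B)* asks about urgency. It is a patient-rated item, not an adverse event, and is not linked to a culture. Section 12.5 plans summaries of the physical and psychological scores only.
- *The culture line in Section 4.1* records an available culture at baseline, follow-up and early discontinuation, apart from the adverse event categories. It can show that a culture was taken. It does not record the symptom, and it gives nothing for a patient who was not cultured.

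None of these says that urgency or frequency is to be recorded when infection is not suspected.

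**Illustration of size.** Only the 12.0% comes from the documents, and treating it as this study's true incidence is itself an assumption. The other inputs are also assumed:

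- s = true non-infective share of symptomatic patients: 30%, 50% or 70%
- f = fraction of non-infective cases not recorded: 0 to 75%
- all infective cases are recorded

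Recorded incidence = 12.0% × (1 − s·f)

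Apparent non-infective share = s(1 − f) / (1 − s·f)

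For s = 0.5 and f = 0.5: 12.0% × (1 − 0.25) = 9.0%, and 0.25 / 0.75 = 33%.

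| f | s = 30% | s = 50% | s = 70% |
|---|---|---|---|
| 0 | 12.0%, share 30% | 12.0%, share 50% | 12.0%, share 70% |
| 25% | 11.1%, share 24% | 10.5%, share 43% | 9.9%, share 64% |
| 50% | 10.2%, share 18% | 9.0%, share 33% | 7.8%, share 54% |
| 75% | 9.3%, share 10% | 7.5%, share 20% | 5.7%, share 37% |

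The first row is the broad reading of the item, under which nothing is lost. The protocol neither fixes f nor rules out a value above zero. The shares here refer to true cause. Cases without a culture would be unclassified in the actual data.

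**The case against.** The best defence is that the item names symptoms and not a diagnosis. It asks for the culture result without requiring a positive one, and the same list elsewhere uses UTI as a diagnosis when it refers to other severe infections. A site could take the item to mean any UTI-like symptom, whatever its cause. That reading matches Section 5.2 and loses nothing. The CRF and the Study Reference Manual are not shown and may say so.

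A second argument is that both groups in Section 5.2 need a culture. In routine practice, a symptom not thought to be infection will often have none. If recorded, it would be unclassified and would not join the culture-negative group.

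Both arguments stand, and they limit the point. A reader might infer that the culture-negative group is in fact under-counted, or that the incidence will come out near the 8.4% placebo rate. The documents support neither. They give no capture fraction, the broad reading gives no bias, and the 12.0% comes from trials whose duration is not stated. Nor is every omitted case beyond recovery, since an available culture is recorded separately.

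What these arguments do not do is settle the meaning of the item. The protocol leaves it undefined and pairs it with a rule that excludes whatever falls outside it.

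**Conclusion.** The collection term and the stated aim do not match clearly, and nothing in the protocol reconciles them. Non-serious urgency or frequency that an investigator does not regard as UTI may go unrecorded, apart from the dosage-change, discontinuation and overdose routes.

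Any loss lowers total incidence. It raises the apparent infective share provided that the omitted symptoms are less often infective than the recorded ones, which is likely when infection was not suspected. The size is unknown and may be zero; the table shows what assumed values would imply and is not an estimate. This is a modest defect, worth correcting because the correction is cheap and omitted symptoms may be unrecoverable.

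**What to change.** Reword the urinary item in Section 11.2.2 along these lines: *urinary tract symptoms (e.g., urgency, frequency, dysuria), whether or not infection is suspected, with urine culture result where available*. Give the CRF a matching prompt. Report the events as culture-positive, culture-negative or not cultured; that tabulation can sit in the SAP.

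The cost is one protocol line, one CRF prompt and somewhat more non-serious reports per site. It adds no procedure, so the study stays noninterventional. Culture remains optional, and many of the added events may fall in the not-cultured group. The third category makes that limit visible but does not remove it.

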injury, may be broadly categorized as excitatory effects in the nervous system, consistent with the K⁺ channel blocking activity of the compound in the nervous system. These AEs include dizziness, paresthesias, insomnia, balance disorders, anxiety, confusion, and seizure. In studies in MS patients, the following most frequent treatment-related AEs were also observed: urinary tract infection (UTI), asthenia, back pain, constipation, dyspepsia, and pharyngolaryngeal pain. At higher dose levels, more severe central nervous system AEs such as confusion and seizure have been seen. With the adoption of the 10 mg twice daily dose in extension studies, the rate of first seizure has been approximately 0.32 per 100 subject-years. This rate does not exceed the expected incidence of seizures in the MS population, particularly in the more advanced disease state with significant ambulatory disability [Eriksson 2002]. However, patients were excluded from these studies if they had a history of seizure or evidence of epileptiform activity on a screening electroencephalogram. Seizures have been seen in the postmarketing setting in the US, although confounding factors such as seizure history and use of concomitant medications that have been associated with a seizure risk may have contributed to the occurrence of seizures in some patients. No new safety signal has been detected as of March 2011.

Please refer to local Fampyra label, product information (PI), or prescription information, e.g., European Summary of Product Characteristics (SmPC) or Australian PI.

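### Confusion is the only excitatory effect named in Section 5.1 without its own collection rule in Section 11.2.2, so its incidence will be incomplete

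*Protocol*

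**What the plan says.** Protocol Section 5.1 describes the most frequent treatment-related events as excitatory effects on the nervous system: "These AEs include dizziness, paresthesias, insomnia, balance disorders, anxiety, confusion, and seizure". It then adds: "At higher dose levels, more severe central nervous system AEs such as confusion and seizure have been seen".

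Protocol Section 11.2.2 sets what sites record. Three categories apply whatever the event term: SAEs, "AEs leading to Fampyra dosage change or discontinuation", and "AEs experienced by the patient at the time of Fampyra overdose". A fourth category, AEs of particular interest, is defined by its sub-items. The one for the nervous system reads "events suggestive of central nervous system stimulation (insomnia, dizziness, paresthesia, balance disorder, dyskinesia, falls, anxiety, sleep disorder, agitation, psychosis, hallucinations, tremor" and continues "trigeminal neuralgia, neuralgia, dysesthesia, sensory disturbance, muscle spasms, muscle twitching, and irritability". Everything else is excluded: "All other non-serious AEs will not be collected as part of this study". The Synopsis (Section 3) repeats this exclusion.

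Seizure has its own rule in Section 11.1.2: "For the purpose of this study, all seizures and spontaneous abortions will be considered SAEs". No such rule exists for confusion.

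**The concern.** The list in Section 11.2.2 turns the known safety profile into a recording rule, and it does not match the profile in Section 5.1. Milder effects such as insomnia, irritability and muscle twitching are collected in every patient. Confusion, one of the two effects that the protocol itself calls more severe, is not. No reason is given.

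The primary objective (Section 6.1.1) covers the incidence of seizure and other specific events of interest. Section 5.2 names patients aged 65 or older as a group that is not yet well understood. Section 12.4 plans person-year rates for AEs of particular interest, and a comparison of event incidence by age group with published data and other sources. A count of confusion restricted to certain routes does not serve those purposes. The omission lies in data collection, so no later analysis can repair it: the events never reach the database.

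**Working it through.** The protocol states no figure for confusion, so the check sets the sections side by side.

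**Step 1. Match the seven effects of Section 5.1 to the collection rules.** The first part of the Section 11.2.2 list has 12 terms and the second has 7: 12 + 7 = 19.

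| Effect in Section 5.1 | Collected whatever its seriousness or consequence? |
|---|---|
| Dizziness | Yes, on the list |
| Paresthesia | Yes, on the list |
| Insomnia | Yes, on the list |
| Balance disorder | Yes, on the list |
| Anxiety | Yes, on the list (and as a separate item) |
| Seizure | Yes, always an SAE (Section 11.1.2) |
| Confusion | No rule of its own |

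Five are listed, one is covered as an SAE and one is left over: 5 + 1 + 1 = 7. The other items of particular interest (urinary symptoms, depression and suicide attempt, cardiac disorders, severe infections, hematologic abnormalities) do not name confusion either.

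**Step 2. Is the list open or closed?** The parenthesis has no e.g., such as or including, and it ends with a final and. Where the protocol means a list to be illustrative, it says so. Section 10.1 uses e.g. for cardiovascular risk factors and marks the list of MS treatments as not exhaustive. The sentence excluding all other non-serious events follows the items of particular interest. Closed is the natural reading, though the protocol does not state it.

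**Step 3. Follow one episode of confusion through the rules.**

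- Serious, including medically important in the investigator's opinion: recorded.
- Leads to a dosage change or discontinuation: recorded.
- Occurs at the time of an overdose, which Section 11.1.3 defines as any dose above the local label: recorded.
- None of these: not on the list, so not collected.

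**Step 4. What this does to the rate.** Count each episode once. Let C be the episodes recorded by one of the three routes, R the remaining episodes, and T the person-years.

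- Rate the study can report: C / T
- Full rate: (C + R) / T
- Shortfall: (C + R) / T − C / T = R / T, which is never negative

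R is not collected, so R / T cannot be estimated from the study. If some sites read the list as illustrative, part of R enters the count at those sites only, and the result is neither C / T nor (C + R) / T.

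**The case against.** **Nothing in the plan is directly contradicted.** No section promises that every event in Section 5.1 will be an event of particular interest. Asthenia, back pain, constipation, dyspepsia and pharyngolaryngeal pain are also named there and not listed. The choice may rest on the risk management plan, which is not at hand. This has some weight, but those five are not excitatory effects. Within the excitatory group, confusion is the sole omission.

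**The dose-related cases are captured.** Section 5.1 ties the more severe confusion to higher doses, and events at any above-label dose are recorded through the overdose route. This stands. A reader might infer that all non-serious confusion is barred from collection; Section 11.2.2 does not support that. The gap is non-serious confusion at the labelled dose with no dosage change or discontinuation.

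**The wider signal is not lost.** A reader might infer that an excess of nervous-system stimulation short of seizure would be missed. The documents do not support this either: a general excess would still show in the 19 listed terms, which include agitation, psychosis, hallucinations and dizziness.

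**The category may be open.** Its governing words are general, nothing says only, and investigators are asked to review all AEs. This is arguable, but then sites may differ, and the incidence is still not comparable.

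**Other reporting routes exist.** Excluded events follow spontaneous reporting rules, and Section 12.6 provides ongoing signal review for patients aged 65 or older. These can raise a signal, but spontaneous reports do not give an incidence.

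**Conclusion.** The point holds in a limited form. Sections 5.1 and 11.2.2 do not agree on confusion, and under the present text the study cannot give a full incidence of it, or one that can be compared with sources that recorded all cases. The part affected is non-serious confusion at the labelled dose that leads to no dosage change or discontinuation.

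The conclusion assumes that sites treat the list as closed, which is a strong inference and not an explicit statement. If sites differ in how they read it, the fault becomes inconsistent recording.

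No number of lost cases should be attached. The protocol gives neither a rate for confusion nor the share that would be recorded through the other routes, so any count would rest on assumption alone. The seizure objective and the sample size in Section 12.7 are unaffected.

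**What to change.** Reconcile Sections 5.1 and 11.2.2 by adding confusion/confusional state to the CNS-stimulation list in Section 11.2.2, and carry the term into the CRF guidance. It is then collected regardless of seriousness and enters the Section 12.4 summaries and person-year rates for AEs of particular interest. Merely stating that the list is illustrative would be weaker, because recording would still depend on each site's judgment.

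The cost is one term and slightly more AE entries, with no new procedure and no change to the sample size. If patients are already enrolled, calculate the rate of confusion from the date of the change, using only events and person-years from that date.
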